5.3 Exclusion Criteria

An individual who meets any of the following criteria will be excluded from participation in this study:

1. Recurrent tumor recommended for surgical resection based on multidisciplinary Head and Neck Oncology Tumor Board Review
2. Thyroid cancer
3. Known hypersensitivity to iodine
4. Other concurrent severe and/or uncontrolled concomitant medical or psychiatric conditions (e.g. active or uncontrolled infection, uncontrolled diabetes) that could cause unacceptable safety risks or compromise compliance with the protocol, per investigator discretion

5. Chemotherapy or major surgery within 4 weeks, or radiotherapy within 2 weeks prior to test dose of CLR 131.
6. Subjects with clinically significant adverse events due to agents administered more than 4 weeks prior to test dose of CLR 131 (alopecia and fatigue excluded). Clinical significance to be determined by investigator.
7. The subject is pregnant, breastfeeding, or expecting to conceive or father children within the projected duration of the trial, starting with the screening visit through 6 months after the last dose of trial treatment.
8. Any ongoing or active infection, including active tuberculosis, hepatitis B or C, or known infection with the human immunodeficiency virus (HIV)
9. Concurrent treatment with any other anti-cancer or investigational agents. Subjects cannot be receiving concomitant chemotherapy, radiotherapy, experimental therapy or any other therapy not otherwise outlined by the trial for the purposes of anti-cancer treatment.
10. Patient with a history of or concurrent second primary malignancy (stage III or IV) within 5 years to study enrollment are excluded.
11. Patients with a history of prior invasive malignancy (except early-stage I or II non-melanomatous skin cancer, carcinoma in situ of the breast, cervical carcinoma in situ, stage I-II papillary thyroid cancer, or low or very low-risk prostate cancer which has been completely treated with surgery or radiation) treated within 2 years of study enrollment are excluded.
12. Subjects that have had total body or hemibody irradiation, or have had prior systemic radioisotope therapy (except for benign thyroid disease)
13. Poor venous access and will be unable to receive study drug into a peripheral venous catheter.
14. Significant traumatic injury within 6 weeks prior to enrollment
15. Extradural tumor in contact with the spinal cord or tumor located where swelling in response to therapy may impinge upon the spinal cord
16. Any history of cerebrovascular accident (CVA) or transient ischemic attack within 12 months prior to study entry
17. History of myocardial infarction, ventricular arrhythmia, stable/unstable angina, symptomatic congestive heart failure, coronary/peripheral artery bypass graft or stenting or other significant cardiac disease within 6 months prior to study entry
18. QT interval corrected for heart rate using Fridericia's formula (QTcF) ≥ 480 ms.
19. Any condition requiring the use of immunosuppression, excluding rheumatologic conditions treated with stable doses of corticosteroids (equivalent to \leq prednisone 10 mg daily)
20. Ongoing hemodialysis or peritoneal dialysis
21. Poorly controlled severe COPD

22. Uncontrolled hypothyroidism or hyperthyroidism
23. Any medical condition that predisposes the subject to uncontrolled bleeding such as hemophilia, factor deficiencies, severe liver disease, or von Willebrand disease.

5.4 Strategies for Recruitment and Retention

The methods used for recruitment of subjects in the study will be devoid of any procedures that may be construed as coercive. The recruitment process will not involve any restrictions on socio-demographic factors, including gender or ethnic characteristics, of the subject population. However, the composition of the study patient population will depend on patient sources available to the clinical site.

Subjects will be recruited from the treating physicians' own clinical practice, through clinic contacts, and referring physicians.

5.4.1 *Subject remuneration*

Subjects will be eligible to receive remuneration to offset the barriers of additional visits required to participate in this study. Subjects are eligible to receive \$50 total for completing the SPECT/CT scan(s) needed following the test dose and an additional \$200 after completing the fourth SPECT/CT scan following the first treatment dose of CLR 131.

5.5 Treatment Assignment Procedures

Subjects who agree to participate and who provide written informed consent will be enrolled via the University of Wisconsin Carbone Cancer Center (UWCCC) Oncore database by the Radiation Oncology research team prior to study-specific participation. All subjects must meet eligibility criteria as listed above. The research staff will verify eligibility, assign a case number, and register the subject in OnCore prior to study-specific participation. The following information will be recorded:

- Protocol number
- Subject's name
- Subject's medical record number
- Subject demographic data

The subject will also be registered with Collectar Biosciences to ensure drug product availability and shipment. Information to be provided to Collectar Biosciences includes: assigned subject identification number, initials, year of birth, body surface area, and dates of planned CLR 131 administration.

5.5.1 *Evaluable Subject*

For evaluation of safety endpoints, any subject that receives any portion of one treatment dose of CLR 131 will be included.

For evaluation of efficacy, subjects must receive all doses of CLR 131 in their entirety and at least one post-infusion efficacy assessment.

5.6 *Subject Withdrawal*

Treatment may continue as specified in the above treatment modality sections or until one of the following criteria applies:

- disease progression;
- intercurrent illness that prevents further administration of treatment;
- unacceptable adverse event(s) (as determined by the subject, treating physician)
- subject decides to withdraw consent for participation in the study;
- subject refuses further treatment (without withdrawing consent for study participation);
- general or specific changes in the subject's condition render the subject unacceptable for further treatment in the judgment of the investigator;
- new data related to the experimental agent which would suggest that continuing treatment on protocol would impose unwarranted potential risks beyond what was known at the time of treatment initiation.
- a female subject becomes pregnant

Subjects will be removed from protocol therapy and the site investigator notified when any of the criteria listed above apply. The reason for discontinuation of protocol therapy will be documented on the electronic case report form (eCRF).

5.6.1 *Handling of Subject Withdrawals or Subject Discontinuation of Study Intervention*

If a subject decides to withdraw from the study (and not just from protocol therapy) all efforts should be made to complete and report study assessments as thoroughly as possible. The subject should be encouraged to complete the withdrawal visit procedures outlined in Section 7.4. A member of the research team should contact the subject or a responsible relative by telephone to establish as completely as possible the reason for the study withdrawal. A complete final evaluation at the time of the subject's study withdrawal should be made with an explanation of why the subject is withdrawing from the study. If the reason for removal of a subject from the study is an adverse event, it will be recorded on the eCRF.

If a subject withdraws from the study prematurely, s/he must continue taking the thyroid-protection medication for 14 days after the last CLR 131 infusion to ensure appropriate protection of the thyroid.

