4 STUDY DESIGN

This is a Phase 1, single center, dose escalation and dose expansion study of subjects with locoregionally recurrent head and neck cancer who may also have distant metastatic disease. All subjects will receive a dosimetry test dose of CLR 131 (flat dose of 15 mCi) to establish drug uptake by the tumor.

Subjects who have tumor uptake of the CLR 131 dosimetry test dose as determined on SPECT/CT imaging by the study radiologist will be eligible to participate on the treatment portion of this clinical trial. Any subject who demonstrates tumor uptake of CLR 131 by SPECT/CT imaging after the test dose will continue to participate in the treatment portion of the study. Up to six participants who do not demonstrate tumor uptake of CLR 131 by SPECT/CT will also continue with the treatment portion of the study. Based on prior experience of subjects receiving CLR 131, 75 % of eligible subjects are estimated to demonstrate CLR 131 uptake within their tumors.

Subjects showing uptake will receive a cumulative tumor dose of 60-70 Gy using personalized dose calculation of CLR 131 (via Monte Carlo) combined with external beam radiation. If the Monte Carlo dose estimate for any subject is greater than 60 Gy for the 2 doses of CLR 131 (highly unlikely based on preliminary data), then no additional external beam dose will be administered.

All subjects will start thyroid-protection medication the day prior to the CLR 131 dosimetry test dose and will continue to take thyroid protection medication for 14 days after the last CLR 131 dose.

Treatment Plan

Enrollment will start at dose level 1. Subjects will receive 2 doses of CLR 131 intravenously with the first dose on day 1 followed by the second dose on day 8. The dose of CLR 131 will be based on the dose escalation schema.

Dose Escalation Schema	
Dose Level	Doses** of CLR 131
-1*	12.5 mCi/m ²
1	15.6 mCi/m ²
2	18.75 mCi/m ²

*Dose level -1 is the de-escalation dose. The first four patients will be given Dose 1. Dose -1 will only be used if toxicities warrant de-escalation.

** Dose level listed is administered first on day 1 and again on day 8.

SPECT/CT imaging will be performed on days 2, 3, 4-6, and 7-8 of the treatment period to visualize and quantitate the biodistribution of CLR 131. Using the SPECT/CT imaging scans, the [name] lab will perform the Monte Carlo calculations to predict absorbed dose of CLR 131 to tumors and normal structures.

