Based on the calculated absorbed dose of CLR 131 to the specific targeted tissue, the subject will undergo EBRT to complete the designated radiation dose outlined in the re-irradiation plan.

At baseline, 3, 6 and 12 months post completion of EBRT, subjects will be assessed for changes to head and neck specific subject health-related measures: quality of life and salivary flow rate. Swallow function will be assessed at baseline, 3 and 6 months post completion of EBRT (standard of care Modified Barium Swallow (MBS) and research-related oral profile exam) see Schematic of Study Design).

Enrollment to the study is anticipated to take approximately 20 months. Each subject will participate for approximately 27 months, although only about four months will be active participation. Details of the study schedule, including lab draws and specific study procedures are provided in section 7.

Incomplete dosing of CLR 131 within study timeframe:

In the event a participant is unable to receive the full study course of CLR 131 within the study timeframe such as a delay in drug manufacturing, the study team will evaluate if it is in the best interest of the study participant to continue with protocol therapy. If it is deemed appropriate for the subject to continue with the CLR 131 administration, their scheduled appointments, labwork and SSKI administration will be adjusted appropriately to accommodate the delay. If it is deemed in the participant's best interest to proceed to SOC EBRT, the following scenarios will occur:

- Only test dose (15 mCi) CLR 131 administered:
 - Continue SSKI until 14 days post CLR 131 administration
 - Proceed with EBRT and SOC follow-up.
- If test dose and a single therapeutic dose are administered:
 - Continue with SSKI until 14 days post CLR 131 administration
 - Undergo imaging for calculations of EBRT dose de-escalation
 - Proceed to EBRT
 - Modify EBRT dose based on the single therapeutic injection
 - Continue follow-up per protocol.

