6.3 Thyroid Protection Medication

To protect the thyroid from uptake of radioactive iodine, administration of thyroid-protection medication is required. Thyroid-protective agents should be administered beginning the day prior to the dosimetry test dose of CLR 131 and continue for 14 days after the last dose of CLR 131.

Thyroid protection medication administration

CLR 131 dose	Duration of thyroid protection medication
--------------	---

Dosimetry test dose only	15 days
Dosimetry test dose +1 Treatment dose	25-30 days, must take 14 days past last dose
Dosimetry test dose +2 Treatment doses	32-38 days, must take 14 days past last dose

Potassium iodide tablets 130 mg orally once daily are the preferred thyroid protection medication. Acceptable alternatives, per institutional preference, include the following:

- Saturated solution of potassium iodide (SSKI) 2 drops orally twice daily
- Lugol's 5 % solution 0.8 mL (approximately 16 drops) orally twice daily

Subjects must receive two doses of SSKI, two doses of Lugol's 5 % solution or one potassium iodide tablet (130 mg) prior to CLR 131 infusion.

If a subject withdraws from the study prematurely, they must continue taking thyroid protection medications for 14 days after the final CLR 131 infusion to ensure appropriate protection of the thyroid.

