9 CRITERIA FOR DISEASE ASSESSMENT

For the purposes of this study, subjects will be evaluated for evidence of response and progression at 3 and 12 months post-completion of the EBRT portion of the protocol – see study calendar. Only those subjects who receive a treatment dose of study drug will be assessed for response and/or progression. Those with inadequate uptake after the dosimetry test dose will only be followed for safety measures.

Response and progression will be evaluated in two distinct fashions. For those without evidence of metastatic disease at the time of study enrollment, response and progression will be evaluated using the new international criteria proposed by the Response Evaluation Criteria in Solid Tumors (RECIST) 1.1 Committee (Eisenhauer *et al.*, 2009).

For those with metastatic disease at the time of study enrollment, study lesions will be defined within the locoregional recurrence field that will be receiving EBRT. Those lesions will be assessed for response and progression using RECIST 1.1 criteria. Lesions outside of the radiation field can be assessed for response to CLR 131 alone. Once palliative systemic therapy is initiated for systemic disease burden, subjects will be censored as having disease progression, regardless of the status of the locoregional target lesions.

Note: Lesions are either measurable or non-measurable using the criteria provided below.

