11.2 Time Period and Frequency for Event Assessment and Follow-Up

Unanticipated problems will be recorded in the data collection system throughout the study.

The PI will record all adverse events with start dates occurring any time after informed consent is obtained until 28 days after the last EBRT treatment or 85 days after first treatment dose of CLR 131, whichever is later. At each study visit, the investigator will inquire about the occurrence

of AE/SAEs since the last visit. Events will be followed for outcome information until resolution or stabilization.

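### The safety set in Section 5.5.1 leaves out subjects who stop after the 15 mCi test dose, so an adverse event that ends participation there is missing from the primary outcome

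*Combined protocol and SAP*

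**What the plan says.** - **Exposure.** Section 4: "All subjects will receive a dosimetry test dose of CLR 131 (flat dose of 15 mCi) to establish drug uptake by the tumor". This comes before the decision on treatment doses.
- **Safety set.** Section 5.5.1: "For evaluation of safety endpoints, any subject that receives any portion of one treatment dose of CLR 131 will be included".
- **Test dose and treatment doses are kept apart.** The table in Section 6.3 has its own row, "Dosimetry test dose only", separate from the rows for one and two treatment doses. The incomplete-dosing text in Section 4 has its own case, "Only test dose (15 mCi) CLR 131 administered", and sends those subjects to EBRT and standard-of-care follow-up. Subjects with one treatment dose stay in per-protocol follow-up.
- **Uptake.** Section 4 assumes that "75 % of eligible subjects are estimated to demonstrate CLR 131 uptake within their tumors", and adds: "Up to six participants who do not demonstrate tumor uptake of CLR 131 by SPECT/CT will also continue" to treatment.
- **Follow-up of the others.** Section 9: "Those with inadequate uptake after the dosimetry test dose will only be followed for safety measures".
- **AE recording.** Section 11.2 starts at consent and runs "until 28 days after the last EBRT treatment or 85 days after first treatment dose of CLR 131, whichever is later". Sections 11.2.1 and 11.2.2 and note 6 of Appendix A give the same window.
- **Primary outcome and analysis.** Section 3.2.1 (AE incidence) and Section 14.3.1 (frequency tables with exact intervals) name no population. Section 14.2 bases outcome analyses on participants treated at the MTD, of whom there are at most 12.

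**The concern.** The primary objective is the safety and tolerability of CLR 131 with EBRT. A safety set would normally include everyone exposed to the study drug. Here, entry to the set depends on getting through the interval between the test dose and treatment dose 1, which Section 7.2.1 targets at 7 to 14 days and allows to reach four weeks. Section 5.6 lets an unacceptable AE or a change in condition end treatment, and does not exempt that interval. Section 11.3.2 expects marrow suppression within four weeks of the first CLR 131 dose.

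A subject who stops in that interval because of an AE leaves both the numerator and the denominator of the primary outcome. With about a dozen subjects in the analysis, one omitted event is visible in the estimate and its interval.

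**Working it through.** The documents give no planned number of test-dosed subjects and no figure for this exclusion, so there is no stated result to reproduce. The check has four steps.

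**1. Does any section restore these subjects?** Section 5.5.1 requires some of a treatment dose. Sections 4 and 6.3 show that the test dose is not a treatment dose. Sections 3.2.1 and 14.3.1 name no wider population, and Section 14.2 names a narrower one. Section 9 provides safety follow-up for subjects without uptake but assigns their data to no analysis set. So nothing restores them.

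**2. How many are excluded for non-uptake?** Inputs: probability of uptake 0.75 and six no-uptake places (Section 4). Assumptions: places are filled in order of arrival, and the total treated, T, lies between 12 and 24, because the documents cap only the number at the MTD.

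- If no no-uptake subject were treated: 12 / 0.75 = 16 test-dosed for 12 treated, so 4 of 16 (25%) have the test dose only.
- With six places: nobody is excluded for non-uptake if at most six of the first T subjects lack uptake, so P(none) = P(Bin(T, 0.25) ≤ 6). Once the places are used, each remaining treated subject costs on average 0.25 / 0.75 = 1/3 of a test-dose-only subject.

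| Total treated (assumed) | Expected test-dose-only | P(none) |
|---|---|---|
| 12 | 0.02 | 0.99 |
| 16 | 0.16 | 0.92 |
| 20 | 0.50 | 0.79 |
| 24 | 1.11 | 0.61 |

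**3. What does one AE-driven stop do?** Exact (Clopper-Pearson) 95% intervals, with assumed counts:

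- 0/12 = 0% (0 to 26.5%); the upper limit is 1 − 0.025^(1/12).
- Adding one test-dose-only subject with an event: 1/13 = 7.7% (0.2 to 36.0%).
- Adding two: 2/14 = 14.3% (1.8 to 42.8%).

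**4. Is the omitted exposure negligible?** The ratio of the test dose to one Dose Level 1 dose is 15 / (15.6 × BSA), with BSA assumed:

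- 1.9 m²: 15 / 29.6 = 51%
- 1.5 m²: 15 / 23.4 = 64%
- 2.5 m² (the dosing cap in Section 6.2): 15 / 39 = 38%

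Section 2.1.3.3 predicts 40 cGy to marrow from 20 mCi. Linear scaling, which is an assumption, gives 40 × 15/20 = 30 cGy. This is more than a tracer amount, although smaller than a treatment dose.

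**The case against.** The best defence is that the test dose belongs to screening and helps to decide eligibility (Sections 5.2 and 7.1), that the objective concerns the combination with EBRT, and that a test-dose-only subject has been treated at no dose level. A treatment-dose set is therefore reasonable for dose-limiting toxicity and MTD summaries. That stands. It does not explain why no table covers everyone exposed.

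Prior experience is also reassuring. Section 2.1.3.3 reports that a single 10 mCi infusion was very well tolerated and that doses up to 25 mCi/m² had no dose-limiting toxicity. Over BSA 2.5 to 1.5 m², the test dose is 6 to 10 mCi/m². An AE-driven stop may therefore be rare, but the documents give no rate.

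Several stronger readings are tempting but not supported:

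- **That test-dose AEs drop out for everyone.** Section 5.5.1 selects subjects, not periods. AEs after the test dose are recorded, and it does not remove them for anyone who later gets some of a treatment dose.
- **That the data are discarded, or a serious reaction would go unseen.** Serious AEs are recorded from consent whether related or not (Section 11.2.2) and go to the DSMC and the company (Section 11.4.2). Section 12 requires cumulative quarterly reports, and the halting rule in Section 11.5 has no treatment-dose condition.
- **That one test-dosed subject in four is lost.** That rate applies only to subjects arriving after the six places are used, or if the places are not used at all.
- **That the bias is always downward.** Only AE-driven stopping clearly acts that way. Non-uptake and supply delay do not depend on toxicity, and adding such lower-exposure subjects could dilute incidence: with assumed counts, 6/12 (50%) becomes 6/16 (37.5%).
- **That test-dose-only subjects have no AE window or assessment.** Those who proceed to EBRT keep the 28-day limit. Section 6.2 requires monitoring during and for one hour after infusion, Section 7.1 lists AE evaluation at screening, and Section 11.2 requires inquiry at each visit. An unmarked test-dose cell in Appendix A does not override these. Only a subject with neither a treatment dose nor EBRT lacks an end date.

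**Conclusion.** The point holds as a gap in the analysis set. Under Section 5.5.1, a subject who stops after the test dose is missing from the primary AE incidence even though the events are recorded. Where an AE caused the stop, the exclusion depends on the outcome and lowers the reported incidence.

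The likely number affected is small: for non-uptake, near zero at 12 treated and about one subject at 24, given 75% uptake and all six places filled in order. If the places went unused, it would be 4 of 16. AE-driven stopping cannot be sized from the documents; the shift of 7.7 percentage points from one subject is an illustration. Oversight during the trial and dose-limiting toxicity decisions are not impaired.

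A separate inconsistency remains. Section 4 sends test-dose-only subjects to standard-of-care follow-up, Section 9 says that those with inadequate uptake are followed for safety, and the recording window has no end for a subject who receives neither a treatment dose nor EBRT.

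**What to change.** 1. In Sections 5.5.1 and 14.3.1, add an all-exposed safety set: every subject given any CLR 131, including the test dose.
2. Tabulate AEs (a) from test dose to treatment dose 1 in all test-dosed subjects, and (b) from treatment dose 1 onward in treated subjects. Separate periods keep lower-exposure subjects from diluting the treatment-period incidence.
3. Keep the treatment-dose set for dose-limiting toxicity and for dose-level (MTD) summaries, and say so beside the MTD sentence in Section 14.2.
4. State where the AE window ends for a subject who receives neither a treatment dose nor EBRT. Reconcile Sections 4, 5.5.1, 9, 11.2, 11.2.1, 11.2.2 and 14.2 and note 6 of Appendix A.

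The cost is wording and one more AE table. The protocol summary gives April 18, 2022 for closure to accrual and June 16, 2022 for the end of the last DLT window, so an extra test-dose visit would yield nothing now. The table can use data recorded since consent. It should state how long test-dose-only subjects were actually followed, since those sent to standard-of-care follow-up may have less complete records.

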7.4 Withdrawal Visit (+ 30 days)

If a subject withdraws or the investigator terminates subject participation prior to 24 months post EBRT, the following tests and procedures will be done:

- Review of concomitant medications
- Physical examination
- Vital signs
- Weight
- ECOG PS
- Adverse event evaluation

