14.2 Sample Size Considerations

An mTPI-2 design, an extension of modified toxicity probability interval (mTPI-2), will be used to identify the MTD using cohorts of 4 subjects and up to 3 dose levels of CLR 131 (Ji *et al.*, 2007; Ji & Wang, 2013). The first 4 subjects will be treated at Dose Level 1. The maximum number of subjects treated at a dose level will be 8, with one exception: if 1 out of 8 subjects experiences a DLT at Dose Level 1, the study team will consider the possibility of treating 2 additional subjects at Dose Level 1. The trial can be monitored using columns 4 and 8 of [Table 3](#) below, which contains the dose-escalation rules. Dose escalation will not be confirmed until all subjects in cohort recover to non-DLT levels or meet the criteria above. If 0 out of 4 subjects experiences a DLT at Dose Level 2, the study will move directly to the expansion phase.

Dose Level	Doses* of CLR 131
-1	12.5 mCi/m ²
1**	15.6 mCi/m ²
2	18.75 mCi/m ²

*Dose level listed is administered on first on day 1 and again on day 8.

**The first 4 subjects will be treated at dose level 1. Dose level -1 will be used as a de-escalation dose.

Table 3: Dose escalation rules

	1	2	3	4	5	6	7	8	9	10
0	E	E	E	E	E	E	E	E	E	E
1	D	D	D	S	S	S	S	S	S	E
2		DU	DU	D	D	D	S	S	S	S
3			DU	DU	DU	DU	D	D	D	D
4				DU	DU	DU	DU	DU	DU	D
5					DU	DU	DU	DU	DU	DU
6						DU	DU	DU	DU	DU
7							DU	DU	DU	DU
8								DU	DU	DU
9									DU	DU
10										DU

Column indicates the number of subjects treated. Row indicates the number of subjects with DLTs. **E**: Escalate to the next higher dose; **S**: Stay at the same dose; **D**: De-escalate to the previous lower dose; **DU**: De-escalate to the previous lower dose and the current dose will never be used again in the trial; sample size = **10**, target toxicity probability = **0.2**, epsilon 1 =**0.1**, epsilon 2 =**0.1**.

The number of participants treated in the expansion cohort is dependent on the number of participants treated at the MTD in the dose escalation phase using the the mTPI-2 design. Up to 12 subjects will be treated at the MTD. Statistical analysis for outcomes is based on participants treated at the MTD, including dose escalation patients treated at the MTD.

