14.3.2 Analysis of Secondary Endpoints

Median radiation treatment time and median number of dose delays due to toxicity will be reported. CLR 131 tumor uptake via SPECT/CT imaging and Monte Carlo calculations will be reported. Quality of life measures (including swallow function assessed by DIGEST scale and

QOL assessed by MDADI score) will be analyzed using frequency tables and confidence intervals constructed using exact statistical methods (such as exact binomial confidence interval) or summary statistics. Comparison of continuous and categorical QOL measures before and after treatment will be described using summary statistics and analyzed using the Wilcoxon signed rank test and McNemar's test, respectively. ORR will be reported as a proportion with an exact confidence interval. Stimulated salivary flow will be reported before and after treatment using summary statistics.

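### Section 5.5.1 ties efficacy evaluability to events after treatment starts, and section 14.3.2 does not say whether ORR uses that set or how unassessed subjects count

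*Combined protocol and SAP*

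**What the plan says.** Four places in the combined protocol and SAP bear on the ORR denominator.

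- **Section 5.5.1** admits a subject to the safety evaluation after any part of one treatment dose. For efficacy, "subjects must receive all doses of CLR 131 in their entirety and at least one post-infusion efficacy assessment". It does not say what counts as an efficacy assessment.
- **Section 14.2** says: "Statistical analysis for outcomes is based on participants treated at the MTD, including dose escalation patients treated at the MTD". It caps that group at 12 and adds no condition on completing treatment or being assessed.
- **Section 9** assesses response and progression only in subjects who receive a treatment dose. It then adds: "Those with inadequate uptake after the dosimetry test dose will only be followed for safety measures". Section 4, however, states: "Up to six participants who do not demonstrate tumor uptake of CLR 131 by SPECT/CT will also continue with the treatment portion".
- **Section 14.3.2** says only: "ORR will be reported as a proportion with an exact confidence interval".

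Section 3.2.2 defines ORR as the share of subjects with a partial or complete response on standard imaging by six months after EBRT, without saying which subjects. Section 4 (incomplete dosing) keeps a subject who received the test dose and a single therapeutic dose in protocol follow-up, with EBRT adjusted for that one dose.

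**The concern.** Whether a subject meets the 5.5.1 conditions is known only after treatment starts, and it can depend on how the subject fares. The stopping reasons in section 5.6 include progression, unacceptable adverse events and "intercurrent illness that prevents further administration of treatment".

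Response imaging is scheduled at 3 and 12 months after EBRT (sections 8.1.18 and 9), so only one nominal scan falls inside the six-month ORR window. The withdrawal visit applies "If a subject withdraws or the investigator terminates subject participation prior to 24 months post EBRT" and lists no imaging (section 7.4). A treated subject who leaves before the 3-month scan may therefore have no response scan at all.

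No sentence counts such a subject as a non-responder. Under 5.5.1 the subject could drop out of the denominator, and the plan does not require the report to show how many left or why.

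ORR is the listed outcome measure for tumor response. Sections 2.2.1 and 14.1 make the maintenance of favorable response rates part of the study hypothesis. At stake is whether the reported rate describes everyone treated or only those who completed dosing and were assessed.

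**Working it through.** **The plan's own figure.** The cap of 12 at the MTD (section 14.2) is the only number that bears on the ORR denominator. The plan states no ORR target, power, interval width or confidence level, so there is no ORR calculation to reproduce. I assume 95% intervals. The documents give neither responder counts nor numbers excluded, so the counts below are assumptions.

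**Which subjects each section would count**

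| Treated subject at the MTD | 14.2 | Section 9, treatment-dose sentence | 5.5.1 |
|---|---|---|---|
| Both doses in full, assessed | in | in | in |
| Both doses in full, no assessment | in | in | out |
| One dose only, followed up | in | in | out |
| No uptake, both doses, assessed | in | in | in |

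The sets differ in the second and third rows. Sections 14.2 and 5.5.1 could also be combined, as the 5.5.1-evaluable subjects within the MTD group. The text does not say so, and that reading keeps the exclusions.

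**Timing of the first scheduled scan.** Three months is about 91 days. With the 4-week window, 91 − 28 = day 63 after EBRT at the earliest.

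**Unassessed non-responders dropped.** With N = 12 treated, r responders and k dropped:

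- all treated: r/N
- 5.5.1 set: r/(N − k)
- ratio of the two: N/(N − k); for k = 2 this is 12/10 = 1.20

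Exact (Clopper–Pearson) limits for r of n are the 2.5% quantile of Beta(r, n − r + 1) and the 97.5% quantile of Beta(r + 1, n − r).

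| Responders | All 12 | 1 dropped | 2 dropped | 3 dropped |
|---|---|---|---|---|
| 4 | 33.3% (9.9–65.1) | 36.4% (10.9–69.2) | 40.0% (12.2–73.8) | 44.4% (13.7–78.8) |
| 6 | 50.0% (21.1–78.9) | 54.5% (23.4–83.3) | 60.0% (26.2–87.8) | 66.7% (29.9–92.5) |

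With two dropped, the shift is +6.7 points for 4 responders and +10.0 for 6. The intervals overlap heavily.

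**One partly dosed subject dropped.** Take 4 responders among the other 11, so the 5.5.1 rate is 4/11 = 36.4%.

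- If the dropped subject did not respond, the all-treated rate is 4/12 = 33.3%, and 5.5.1 is 3.0 points too high.
- If the dropped subject did respond, it is 5/12 = 41.7%, and 5.5.1 is 5.3 points too low.

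The direction is unknown because this subject still receives EBRT and may respond.

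**The case against.** The strongest reply is that the plan already points to an all-treated denominator. Section 9 assesses anyone given a treatment dose, section 14.2 uses all participants at the MTD, and neither 3.2.2 nor 14.3.2 invokes 5.5.1 for ORR. On that reading, a treated subject with no observed response is simply absent from the numerator. This stands in part. A reader might infer that the plan, as written, removes unassessed subjects and so inflates ORR. The documents do not settle that; it follows only if 5.5.1 is applied. But 5.5.1 is the one place that defines evaluability for efficacy, and nothing says it gives way.

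Other points on that side:

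- **Undefined assessment.** Physical examinations take place one month after the first treatment dose and at withdrawal, and section 9.3 allows superficial lesions to be measured clinically. If such an examination qualifies, an early leaver stays evaluable. The protocol does not say, so the ambiguity remains.
- **Little time for outcome-driven missed doses.** The treatment doses are on days 1 and 8, and the documents' own example of incomplete dosing is a manufacturing delay. This is fair. The selection concern rests mainly on the assessment condition.
- **Efforts to limit missing data.** Section 5.6.1 urges complete assessment at withdrawal, and section 8.1.18 allows clinically indicated scans. These reduce the number of unassessed subjects but do not say how the rest are counted.

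A reader might also infer that section 9 removes treated no-uptake subjects and could halve the denominator, for example from 4/12 to 4/6 = 66.7% (22.3–95.7). In context, that sentence most naturally describes subjects who received only the test dose. The example also needs all six at the MTD and every responder to have uptake; with equal response in both groups the rate stays at 2/6 = 33.3%. This is a wording repair.

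Section 9's rule on starting palliative systemic therapy concerns progression, and is not evidence on the ORR denominator.

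**Conclusion.** The concern holds in conditional form. The plan contains three population statements that are not reconciled, one of which depends on events after treatment starts, and it has no rule for unassessed subjects. If 5.5.1 governs ORR and the unassessed did not respond, ORR is raised by the factor N/(N − k): 1.20 for two of 12. Excluding partly dosed subjects can move it either way.

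These sizes rest on assumed responder and exclusion counts, a full group of 12 and 95% intervals. At this sample size, sampling imprecision exceeds the shift. ORR is secondary and descriptive, with no test or threshold, and safety evaluability needs only part of one treatment dose, so the primary safety conclusion is unaffected.

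The documents do not support a claim that the reported ORR will be inflated. They support the narrower statement that different denominators can be defended after the fact. The change should be made, because it is cheap and removes that choice.

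**What to change.** 1. In 14.3.2, report ORR over all subjects at the MTD given any treatment dose. Count anyone without a documented partial or complete response by six months after EBRT as a non-responder.
2. Show the 5.5.1 set beside it as a sensitivity analysis, with the number excluded and the reason for each (incomplete dosing or no assessment). State in 5.5.1 what counts as an efficacy assessment, so that this set can be formed.
3. Reword section 9 so that the inadequate-uptake sentence refers to subjects who were not treated, and show the responses of treated no-uptake subjects separately.
4. Date the change and label it as made after accrual closed. The Protocol Summary gives April 18, 2022, so response data may already be known, which is why both rates should be shown.

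**Cost.** No new subjects, scans or data. The wording is protocol text, so section 17.2 requires an IRB-approved amendment. The all-treated ORR may be lower than the 5.5.1 figure, or higher if partly dosed subjects responded.
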